### 1 Background

The main goal of providing early hearing aids in childhood is to ensure that the child's language development is as normal as possible. However, children's hearing needs change as they grow older. A growing child is exposed to many new listening environments, which often include multiple sound sources and loud everyday noises. In such situations it can sometimes be very difficult for the child to understand speech clearly. The older a child gets, the more often communication usually takes place in acoustically complex environments in which the audibility of the speech signal can be significantly impaired. Numerous studies show that poor acoustic conditions impair the speech intelligibility of children with normal hearing more than that of adults with normal hearing (McCreery et al., 2010; Wroblewski al., 2012; Yang & Bradley, 2009). In addition, poor acoustic conditions have a negative impact on children's ability to learn and thus their academic success (Dockrell & Shield, 2004; Klatte, Hellbrück, et al., 2010).

Speech recognition and speech understanding in noisy environments is a challenge for people who are hard of hearing, but it is particularly difficult for children and young people. Especially in learning situations, directional microphones and noise cancellation functions in hearing aids can lead to improved speech recognition when speech and noise come from different directions.

However, these technologies offer only limited benefits and in certain cases the use of, for example, a directional microphone hearing aid mode can also have a detrimental effect. In recent years, initial studies have been carried out on the usability of directional microphone systems and noise suppression functions in pediatric care. However, so far there is little evidence about directional microphone use, spatial hearing and the possible benefits of directional microphones in children's everyday environments. The few studies that have been carried out so far also show contradictory results. While one study shows (Ching et al., 2009) that directional microphones are more effective than omnidirectional microphones in speech recognition when speech comes from the front and background noise occurs directly behind the listener, another study shows that omnidirectional microphones are more effective, when language comes from different directions, which is quite often the case with younger children, as they often have a different "head position" when listening than adults. In one study, half of the children preferred directional microphones in most situations, whereas the other half preferred omnidirectional microphones (Ricketts et al., 2007). In another study, both children and parents rated both types of microphones equally well (McCreery et al. 2010).

Nowadays almost all modern hearing aids have automatic systems (e.g AutoSense), which are able to independently control the change between omnidirectional microphones and directional microphones. Overall, it appears that directional microphones can be useful in some of the many different acoustic environments that children and young people are exposed to, either at home, at school or in social situations. However, there are also situations in which directional microphones may not be advantageous or may even be disadvantageous (Wolfe et al., 2017). This applies both to adaptive systems in which the hearing aid makes the selection itself (AutoSense) and to systems in which the child is supposed to make the decision himself.

It is believed that directional microphones and noise cancellation functions could also

be beneficial for children and young people in general if there is more detailed knowledge about the extent and in which environments children need these functions. This study is intended to help understand when, to what extent and at what age these functions are beneficial for children and young people in order to be able to adapt the design of these functions and thus the programming of hearing aids more individually to children and young people.

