## **2 Objectives**

The primary objective is to evaluate the impact on speech intelligibility resulting from the changes that children and adolescents (aged 7 to 17 years) make to the microphone directionality and noise cancellation of their hearing aids using the myPhonak app.

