## 6 Endpoints

The primary endpoint will be the difference in SRT- 50 levels using the adaptive Oldenburg Sentence Test (OLSA) between the following conditions:

1. Hearing aid Autosense Sky OS
2. Hearing aid Preferred setting (manual adjustments to the Noise Reduction and Directionality)
3. Hearing aid extreme setting with the Noise Reduction set to maximum and the Directionality set to minimum.

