### Inclusion Criteria

- Children and adolescents between the ages of 7 and 17 years old.
- Bilateral mild to severe hearing loss
- Experienced hearing aid users for 6+ months

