## 8 Measurements and procedures

The investigation will have two lab visits and one home trial. The procedures are as follows:

Visit 1	Home Trial ~ 2 weeks	Visit 2

Audiogram, if needed
 
Obtain informed consent from parents
 
Fit study devices to match that of personal devices, verified with coupler measurements
 
Download myPhonak Jr app to personal or loaner smartphone and pair with
	
Participant instructed to use the app in five different situations and rate the ease of each situation, using the Assessment of hearing situations in children's every day lives".- To be completed after one week, and then after the second week.
	
Repeat dB SNR testing using OLSA (randomized order):
 
 
1. AutoSense Sky OS
 
2. Preferred Setting
 
3. Extreme setting
 
 
Interview and discussion of questionnaire results

study hearing aids
 
Train on app use
 
dB SNR obtained using the OLSA test with study devices in the following conditions: (randomized order):
 
 
1. AutoSense Sky OS
 
2. Preferred Setting
 
 
Extreme setting Give 2 copies of “Assessment of hearing situations in children’s every day lives” to complete during home trial
		
---	--	--

The test environment is set up as follows:

Cafeteria noise at 65 dBA, from four speakers (-50°, +50°, -130°, +130°)  
 Speech presented at 70 dBA, from front speaker (0°)

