## **9 Statistical design and analysis**

The variance known from the OLSA manual between normal hearing subjects aged 7-9 years is 3 dB, and 1.5 dB for adults over the age of 18.

A significance level of 0.05, a power of 0.8 and the approximate variance of 3 dB, a sample size of 24 is needed.

A non-parametric RM-ANOVA will be used for comparing the group OLSA results for the different conditions. Durbin-Conover pairwise comparisons will be used for post hoc analysis.

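### Does the age question raised in the Background oblige the plan to analyse results by age?

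*Combined protocol and SAP*

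**What the plan says.** Section 1 (Background) closes with a statement of purpose: "This study is intended to help understand when, to what extent and at what age these functions are beneficial for children and young people". It links this to programming hearing aids more individually for young users.

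Section 2 gives one formal objective: "The primary objective is to evaluate the impact on speech intelligibility resulting from the changes that children and adolescents (aged 7 to 17 years") make with the app. Age appears there only to describe who takes part. Section 6 defines the endpoint: "The primary endpoint will be the difference in SRT- 50 levels using the adaptive Oldenburg Sentence Test (OLSA) between the following conditions", followed by AutoSense, Preferred and Extreme. Section 7 admits "Children and adolescents between the ages of 7 and 17 years old", with no age strata or quotas.

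Section 9 is the whole statistical plan: "A non-parametric RM-ANOVA will be used for comparing the group OLSA results for the different conditions", followed by Durbin-Conover pairwise comparisons of the conditions. Its only other mention of age is in the variability figures used for the sample size: "The variance known from the OLSA manual between normal hearing subjects aged 7-9 years is 3 dB", with 1.5 dB given for adults. No section plans an age covariate, subgroup or plot.

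**The concern.** A reader who takes Section 1 as a list of study questions will look for an analysis of age and find none. Section 9 compares conditions within child and then pools over children, so a benefit confined to younger or older participants would be averaged into one result.

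The protocol also gives its own reasons to care about age. Section 1 says that hearing needs change as children grow and that speech often reaches younger children from directions other than the front. Section 9 cites different variability for young children and adults.

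Two things would be at stake. The study as planned would not show differences by age within 7 to 17. If a report nevertheless commented on age, the contrast, visit and model behind the comment could have been chosen after the data were seen.

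**Working it through.** **1. Which sections set the question.** Taken side by side:

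- Section 1: broad purpose, includes age.
- Section 2: effect on speech intelligibility of the users' own adjustments, ages 7 to 17 together.
- Section 6: SRT-50 differences between three conditions, no age contrast.
- Section 9: pooled comparison of those conditions.

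Sections 2, 6 and 9 agree with one another. Only the Background is broader.

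**2. The plan's own figure.** The sample size of 24 cannot be rebuilt forward, because Section 9 gives no effect size, sidedness or within-child correlation, and its 3 dB may be a variance or an SD. Working backwards with two-sided alpha 0.05 and power 0.80, the detectable pooled difference is (1.960 + 0.842) × SD / √24:

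- SD 1.73 dB (3 read as a variance): 2.802 × 1.732 / 4.899 = 0.99 dB
- SD 3 dB (3 read as an SD): 2.802 × 3 / 4.899 = 1.72 dB

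Both SDs are assumptions. Section 9's figure describes spread between normal-hearing children aged 7 to 9, whereas the calculation needs the SD of a within-child difference in hearing-impaired children.

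**3. What an age slope could deliver.** Assume 24 ages evenly spaced over 7 to 17. The spacing is 10/23 years, so Sxx = (10/23)² × 24 × (24² − 1)/12 = 217.4, with √Sxx = 14.74. With t(0.975, 22 df) = 2.074, the 95% half-width for the trend over 10 years is 10 × 2.074 × SD / 14.74 = 1.41 × SD. If ages cluster with an SD of 2 years, Sxx = 23 × 4 = 92 and the half-width is 10 × 2.074 × SD / √92 = 2.16 × SD. Power is two-sided, from the noncentral t with 22 df, for an illustrative trend of 0.1 dB per year (1 dB over 10 years). Neither that trend nor the age spread comes from the documents.

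| Assumed SD of difference (dB) | Half-width, even ages (dB) | Half-width, clustered ages (dB) | Power, even ages |
|---|---|---|---|
| 1 | 1.41 | 2.16 | 29.2% |
| 1.73 | 2.44 | 3.74 | 12.9% |
| 3 | 4.22 | 6.49 | 7.6% |
| 4 | 5.63 | 8.65 | 6.4% |

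**4. Two age groups instead.** With 12 younger and 12 older children, the detectable difference in benefit is 2.802 × SD × √(2/12). That is 1.98 dB for SD 1.73 and 3.43 dB for SD 3, twice what the pooled sample detects. Power for an age difference as large as the pooled detectable effect is about 29%. Reaching 80% would need 48 per half, 96 in all.

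**5. What the contrast measures.** Section 1 describes AutoSense as an automatic system that itself switches between omnidirectional and directional microphones. Preferred minus AutoSense therefore sets the child's manual choice against automatic control. The Extreme condition raises noise reduction and lowers directionality together. None of the three pairs isolates the benefit of one function, so a slope of any of them on age would not answer the Background's question directly.

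**The case for a change.** The strongest case for a change is that the Section 1 sentence says what this study is for, not what the literature says, and that bringing purpose and plan together is cheap. One exploratory regression of the Visit 2 Preferred-minus-AutoSense difference on age would use data already planned and would fix the contrast and visit in advance. If that were judged too imprecise, deleting the age phrase would do. On this view, imprecision argues for deletion and not for leaving the text alone.

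Some of this stands. The mismatch exists, Section 9 would not show differences by age within the enrolled range, and any age comment in a report would be exploratory.

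The rest does not carry the point:

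- The regression would require choices the documents do not make. Section 6 ranks no pair of conditions, and Section 8 tests all three at both visits. A straight line also need not answer a question that may concern a threshold.
- Deleting the phrase alters no analysis or result. The same sentence also promises to show when the functions help, which is no better covered: Section 8 uses one laboratory noise set-up and states no analysis for its questionnaire.
- It is too strong to say the study would be silent on age. A result in 7-to-17-year-olds is evidence about that age band, which Section 1 contrasts with adults.
- The harm is conditional. No section, including the publication policy in Section 19, plans a claim about age.

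**Conclusion.** No change is called for. This is a Background statement wider than the plan, and the sections that govern the analysis agree with one another. The pooled comparison suits the objective and endpoint, and no planned conclusion would be wrong because age is left out.

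The gain from adding an age analysis would be small. For assumed SDs of 1.73 to 3 dB with ages evenly spread, the interval for a 10-year trend is ±2.4 to ±4.2 dB, about 2.5 times the difference that the pooled comparison can detect at the same SD (0.99 to 1.72 dB). Over all the SDs and age spreads tried it runs from ±1.4 to ±8.6 dB. Such an estimate could not exclude a modest age effect, and it would concern manual versus automatic control, not the functions themselves.

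These sizes rest on assumed SDs, age distributions and a 1 dB illustrative trend. The conclusion does not depend on them, since it follows first from age being absent from Sections 2 and 6. Analysts can fill the gap sensibly by plotting within-child differences against age, calling the plot exploratory and drawing no age conclusion from it.

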## **2 Objectives**

The primary objective is to evaluate the impact on speech intelligibility resulting from the changes that children and adolescents (aged 7 to 17 years) make to the microphone directionality and noise cancellation of their hearing aids using the myPhonak app.

## **3 Description of the investigational device**

The devices used in this study are CE certified and commercially available: Phonak Sky M90-M or Sky M90-SP hearing aids and the myPhonak app. These are manufactured and maintained by Sonova, AG located in Stafa, Switzerland.

The overall intended purpose of the hearing aid device is to amplify and transmit sound to the ear and thereby compensate for impaired hearing. The myPhonak app is an accessory to a medical device (hearing aid with wireless functionality). It is used as a remote control to a hearing aid. The app is a software application which is installed and used on a smartphone with an Apple iOS or with an Android OS. The myPhonak app allows the end-user to adjust certain parameters of Phonak hearing aids, such as volume, program changes, microphone directionality, and noise reduction and is intended for use with compatible Android or Apple iOS devices. The app itself is classified as a medical device (class II) but is not needed to enable the hearing aids to be used according to their intended purpose.

## **4 Design of the clinical investigation**

This investigation is a single-group, single site, interventional study.

## **5 Risks and benefits of the investigational device and clinical investigation**

There are minimal risks associated with both the investigational device and participating in the clinical investigation. Identified risks are no greater than those associated with the daily use and wear of approved, available hearing aids. The device used presents non-significant risk per FDA. The benefits of participating in the investigation include the possibility of hearing sounds that have not been previously heard, such as speech and environmental sounds, which may improve communication in daily life. Subjects may experience the benefit of personal satisfaction for participating in research to improve hearing instrument technology. Subjects will also be compensated for their time in participating in this study.

There are no known or anticipated risks to subject hearing ability associated with participation in this study. All sounds used in this study will be presented at safe listening levels. While using hearing aids, the following are possible occurrences:

- Cerumen impaction
- Ear discomfort, pain or soreness
- Sweat or moisture accumulation in the ear canal or pinna

- A feeling of pressure or fullness in the ear
- Itching, blisters, or sores in the ear canal or pinna
- Headache
- Redness of tissue

The research personnel will review these risks with the subjects and answer any questions they have. Hearing aids are not a significant risk investigational device as defined in the FDA 21 CFR 812.3(m).

## 6 Endpoints

The primary endpoint will be the difference in SRT- 50 levels using the adaptive Oldenburg Sentence Test (OLSA) between the following conditions:

1. Hearing aid Autosense Sky OS
2. Hearing aid Preferred setting (manual adjustments to the Noise Reduction and Directionality)
3. Hearing aid extreme setting with the Noise Reduction set to maximum and the Directionality set to minimum.

## 7 Inclusion and Exclusion Criteria

The participants will be recruited from the clinic's patient population.

### Inclusion Criteria

- Children and adolescents between the ages of 7 and 17 years old.
- Bilateral mild to severe hearing loss
- Experienced hearing aid users for 6+ months

### Exclusion criteria

- Any additional disabilities to the hearing impairment
- Inability to complete the study procedures

## 8 Measurements and procedures

The investigation will have two lab visits and one home trial. The procedures are as follows:

Visit 1	Home Trial ~ 2 weeks	Visit 2

Audiogram, if needed
 
Obtain informed consent from parents
 
Fit study devices to match that of personal devices, verified with coupler measurements
 
Download myPhonak Jr app to personal or loaner smartphone and pair with
	
Participant instructed to use the app in five different situations and rate the ease of each situation, using the Assessment of hearing situations in children's every day lives".- To be completed after one week, and then after the second week.
	
Repeat dB SNR testing using OLSA (randomized order):
 
 
1. AutoSense Sky OS
 
2. Preferred Setting
 
3. Extreme setting
 
 
Interview and discussion of questionnaire results

study hearing aids
 
Train on app use
 
dB SNR obtained using the OLSA test with study devices in the following conditions: (randomized order):
 
 
1. AutoSense Sky OS
 
2. Preferred Setting
 
 
Extreme setting Give 2 copies of “Assessment of hearing situations in children’s every day lives” to complete during home trial
		
---	--	--

The test environment is set up as follows:

Cafeteria noise at 65 dBA, from four speakers (-50°, +50°, -130°, +130°)  
 Speech presented at 70 dBA, from front speaker (0°)

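### Do the single speech (70 dBA) and noise (65 dBA) levels in Section 8 prevent the adaptive SRT-50 from being measured?

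*Combined protocol and SAP*

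**What the plan says.** Section 6 defines the outcome: "The primary endpoint will be the difference in SRT- 50 levels using the adaptive Oldenburg Sentence Test (OLSA) between the following conditions". The three conditions are the automatic program, the child's preferred setting and an extreme setting.

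Section 8 describes the testing. At Visit 1 the plan has "dB SNR obtained using the OLSA test with study devices in the following conditions", and at Visit 2 "Repeat dB SNR testing using OLSA (randomized order". Below the visit table it lists the acoustic set-up: "Cafeteria noise at 65 dBA, from four speakers" placed around the listener, and "Speech presented at 70 dBA, from front speaker (0" degrees). Neither level is described as constant, initial or varying. The section does not name the signal that is adapted, the step rule, or whether 65 dBA is the total of the four loudspeakers or the level of each.

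Section 9 plans on the same scale: "A significance level of 0.05, a power of 0.8 and the approximate variance of 3 dB, a sample size of 24 is needed". Section 4 states that the study has one group and one site.

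**The concern.** An adaptive threshold exists only if the SNR moves from sentence to sentence until half the speech is understood. A set-up that lists one number for speech and one for noise looks like a fixed-SNR test. Run that way, the trial would record percent correct at +5 dB and the primary endpoint would not be measured. If that SNR were easy for the children, scores would bunch near the top and hide differences between settings.

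A second worry remains even if the test is adaptive. The settings differ in noise reduction and directionality, and both act on the incoming sound. Holding the noise and moving the speech is not acoustically the same as the reverse. A tester who changed the rule between runs could add error to the within-child differences.

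**Working it through.** **Inputs.** Speech 70 dBA and noise 65 dBA from four loudspeakers (Section 8); adaptive test and SRT-50 (Section 6); planning variance in dB (Section 9). The documents give no psychometric slope and no expected threshold. The only derived figure in the plan is the sample size of 24, and this point does not depend on it.

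**Step 1: nominal SNR.** If 65 dBA is the combined noise level, SNR = 70 - 65 = +5 dB. If it is the level of each loudspeaker and the four sources are incoherent, the combined noise is 65 + 10 x log10(4) = 65 + 6.02 = 71.02 dBA, and SNR = 70 - 71.02 = -1.02 dB.

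**Step 2: what a fixed SNR would give.** Assume a logistic curve, score = 1 / (1 + exp(-4 x slope x (SNR - SRT))). Slope and SRT are assumptions.

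| SNR (dB) | Slope per dB | SRT (dB) | Score |
|---|---|---|---|
| +5 | 0.10 | 0 | 1/(1 + exp(-2.0)) = 88% |
| +5 | 0.15 | 0 | 1/(1 + exp(-3.0)) = 95.3% |
| +5 | 0.15 | -1 | 1/(1 + exp(-3.6)) = 97.3% |
| +5 | 0.15 | -5 | 1/(1 + exp(-6.0)) = 99.8% |
| +5 | 0.10 | +3 | 1/(1 + exp(-0.8)) = 69% |
| +5 | 0.10 | +5 | 1/(1 + exp(0)) = 50% |
| -1.02 | 0.10 | 0 | 1/(1 + exp(0.408)) = 40% |

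The ceiling appears in the first four rows, where a 1 dB change in threshold (rows two and three) moves the score by 97.3 - 95.3 = 2 points. It is absent in the last three. Section 7 admits children with mild to severe loss, so the documents do not exclude thresholds above 0 dB. Even for a fixed-SNR test, a ceiling is possible but not established.

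**Step 3: is a fixed-SNR test what the plan describes?** Section 6 names the adaptive test and a 50% threshold. Section 8 twice makes dB SNR the thing measured, which would be pointless if SNR were set in advance. Section 9 gives variability in dB, the unit of a threshold. No passage mentions percent correct. The only support for a constant SNR is that Section 8 does not label its levels.

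**Step 4: what the missing detail can change.**

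- *Combined or per-speaker level.* If this affects only how SNR is recorded, every threshold shifts by the same c = 6.02 dB. The endpoint is a difference, and (SRT_A + c) - (SRT_B + c) = SRT_A - SRT_B. The within-child ranks used by the non-parametric analysis in Section 9 do not change either.
- *Which signal moves.* Take 65 dBA as combined and let the threshold be x dB SNR. Noise held: noise 65, speech 65 + x. Speech held: speech 70, noise 70 - x. At the same SNR both signals differ between the two rules by 5 - x dB, which is 5 dB at x = 0 and 10 dB at x = -5. Presentation level differs, but each rule yields a valid SRT-50, and the three settings are compared under the same rule.

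**The case for a change.** The strongest reply is that the adaptive reading has to be supplied by the reader, and that two procedures fit the text: noise held at 65 dBA with speech moving, or speech held at 70 dBA with noise moving. Step 4 shows that they can differ by several decibels in presentation level. The Background section says that the automatic program chooses its own microphone mode, so the level at which it is tested might affect how it behaves. One sentence would settle the matter at almost no cost.

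The description of the gap stands: Section 8 does not name the adapted signal, the start level or the step rule. The harm is not shown. Nothing in the plan leaves the rule to the individual tester or lets it vary. There is one site, and the second visit is described as a repeat of the first. At each visit all three settings are tested in randomized order, so a change of rule between visits would not by itself favor one setting within a visit. Moving either signal alters the mixture that reaches the hearing aid, so naming one of them would not remove that feature of adaptive testing. The documents also give no basis for preferring one rule to the other.

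**Conclusion.** The concern does not call for a change. The plan names an adaptive threshold test and treats dB SNR as its result. The +5 dB figure is arithmetic on two set-up levels, not a stated constant. The 88% to 100% scores belong to a test that the plan does not describe, and they require a slope of 10% to 15% per dB, a threshold between -5 and 0 dB, and 65 dBA as the combined noise level. The same formula gives 40% to 69% under other inputs that the documents do not exclude.

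What survives is a reporting gap that a site running the named test fills when it configures the test. Its effect on the within-child difference is nil for a recording offset. For the choice of adapted signal the effect cannot be sized from the documents, but that choice does not prevent a valid comparison. This conclusion assumes that the site uses one rule for all three settings at both visits, which is how the plan's description of repeated testing reads.
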